#### Myalgias and Myopathy

Significant myalgias (Grade  $\geq 3$ , i.e., muscle pain causing inability to perform usual social and functional activities) should be evaluated with a clinical assessment that includes an evaluation of CK, serum

creatinine, potassium, and urinalysis. Myopathy is defined as muscle aches, soreness, tenderness, or weakness with creatinine kinase (CK)  $>10$  x ULN not related to exercise or other causes, including trauma. If the symptoms are associated with Grade  $\geq 3$  elevation in CK (10 x ULN) that is not related to exercise or other cause, study medications should be permanently discontinued. Participants will be followed on study, off study drug treatment through the study termination visit per protocol.

#### Other toxicities

Grade 1 toxicities: In general, for grade 1 toxicities, the patient will be followed carefully, and the study drugs will be continued.

Grade 2 toxicities: For grade 2 toxicities, the patient will be followed more carefully, with additional laboratory and/or clinic visits as necessary, and the study drugs temporarily held at the investigator's discretion.

Grade 3 toxicities: For any grade 3 toxicity involving creatinine kinase elevation, with or without myopathy, myalgias, hepatitis, nausea/vomiting, and/or diarrhea, that, in the principal investigator's judgment is due to study drug, the study drug will be discontinued. The clinician should rule out other possible causes of the symptoms before discontinuing study medication. When possible, concomitant medications should be held first at the discretion of the principal investigator if he/she suspects they are contributing to the toxicity. In the event of study product discontinuation, management of the standard of care TB drugs will revert to the site clinician as per local practice.

Grade 4 toxicities: Any patient with grade 4 renal, hepatic, cardiac or hematological toxicity will be immediately discontinued from study therapy. The laboratory test or clinical finding in question will be reassessed as soon as possible. The repeat test will guide management of the event as follows:

- If the repeat assessment shows toxicity of grade 3 or lower, and if the patient has continued to receive study drugs between the two testing dates, then the patient will be managed according to the appropriate toxicity level of the repeat test.
- If the repeat test shows toxicity of grade 3 or lower, and if the participant has not received study drugs between the two testing dates, then the participant will be managed at the discretion of the investigator with regard to the re-administration of study drugs, and otherwise according to the toxicity level of the repeat test.
- If the repeat test shows grade 4 toxicity, then the participant will be permanently discontinued from study medications. Further treatment of TB will be directed by the investigator on an individualized basis. The participant will continue to be followed for study monitoring purposes (as are other participants who make a permanent departure).

For other grade 4 toxicities, the study drugs will be permanently discontinued. Toxicities graded 3 or 4 and occurring during study therapy will be documented on the AE Form, according to the criteria described in the following sections. The maximum level of toxicity reached will be clearly indicated.

For all toxicities that are treatment-emergent and that require permanent discontinuation of study treatment, relevant clinical and laboratory tests will be obtained as clinically indicated and repeated as needed until final resolution or stabilization of the toxicity.

**Permanent discontinuation of study drugs:** Certain events or conditions may necessitate permanent discontinuation of the statin study drug. Participants who experience such events or conditions, however, will still be "on study" and will be followed until study completion. Study drug will be discontinued with continued study follow-up for participants in whom treatment-emergent drug toxicity warrants discontinuation of study therapy and for participants who become pregnant. If study drug is permanently

discontinued, continued standard-of-care therapy for tuberculosis may be administered at the investigator's discretion. If Rifafour is discontinued, the individual components (isoniazid, rifampin, pyrazinamide, and ethambutol) may be gradually re-introduced, as per national guidelines.

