### ***Safety and Tolerability Endpoints***

The primary endpoint for analysis of safety and tolerability is Grade 3 or higher adverse events. Secondary endpoints include permanent discontinuation of assigned study regimen for any reason (other than new recognition of participant ineligibility based on absence of *M. tuberculosis* growth in baseline sputum cultures, or growth of *M. tuberculosis* resistant to rifampin by GeneXpert. Other aspects of safety and tolerability that will be assessed include mortality and the rates and types of toxicity thought related to study drugs by the Investigator.

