### ***Reporting***

**AE:** Adverse events (AE) will be collected by the Investigators from the time a study participant receives the first dose of study drug through the Day 30 study visit. Any AE (serious or non-serious) observed by the Investigator or reported by the study participant that meets the AE reporting requirements (see below) will be recorded on an Adverse Event Case Report Form. The Investigator will review each AE and assess its relationship to drug treatment based on all available information at the time of the completion of the case report form. The following information will be recorded for each AE reported:

- Diagnosis of the AE, if possible. In the case where an overall diagnosis cannot be made, each specific sign and/or symptom will be recorded as individual AEs;
- Date of onset;
- Stop Date (duration) if applicable;
- Severity;

- Action taken with study drugs;
- Other action taken;
- Outcome;
- Relationship to study drugs;
- Seriousness.

The following adverse events must be reported on an Adverse Event Report Form:

- New medical diagnosis (at the time of enrollment, if the patient already has a medical diagnosis whose signs or symptoms worsen during the study to a Grade 3 or 4, this is an adverse event that must be reported)
- Any grade 3 or higher adverse event
- Study drug discontinuation due to an adverse event
- Pregnancy
- Lab values that are considered clinically significant by the investigator

The standard-of-care drugs are Rifafour (Ethambutol, Isoniazid, Rifampin, and Pyrazinamide) and the study drug is pravastatin. The most common adverse effects associated with the standard-of-care drugs and the study drug are specified in the "[Study Drugs](#)" section. The Investigator is responsible for monitoring all adverse events that are observed or reported during the study, regardless of whether they are related to the study drug. Participants presenting with AEs to other facilities during the study period will be referred back to the study site in order to complete all study visits and data collection. The participant will be given instructions to notify the study team if any AEs develop following the study period.

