**9. Definition of treatment failure or participant removal criteria.**

Participants who prematurely discontinue study treatment after having received one or more doses of pravastatin will be replaced.

Study treatment must be immediately discontinued as a result of the following:

- Withdrawal of informed consent.
- Investigator considers it for safety reasons in the best interest of the participant that he/she be withdrawn.
- If a participant develops a new onset stage 4 illness after enrollment, they would meet the criteria for withdrawal from the study and, if HIV-positive, for fast track initiation of ART per the South African National Department of Health ART guidelines. The Interim WHO Clinical Staging of HIV/AIDS and HIV/AIDS Case Definitions for Surveillance, African Region (2005) will be used for guidance on definitions of stage 4 illnesses.
- Resistance to rifampin, as determined by GeneXpert.
- Participant experiences specific toxicities (including liver toxicity, CK elevation and myalgias and myopathy, as outlined in the "[Clinical Management of Adverse Events](#)" section)
- Participant becomes pregnant.
- Termination of the study by the Sponsor (US FDA, OHRP, or other relevant regulatory agencies)
- Non-compliance with the study protocol (missing more than 2 doses of study drugs or not completing one of the PK sampling visits)

All participants discontinuing study drug due to severe AE will remain in the study and continue to be monitored until the final scheduled clinic visit/laboratory evaluation. Their treatment will be referred to the local community TB clinics for standard anti-tuberculosis chemotherapy according to National Guidelines. The participants will be provided with a referral letter to take with them to the TB Clinic. Participants will be transported by the study staff to the clinic, or a follow-up call will be made by the study site staff to the clinic to determine if the participant attended the clinic on the date as arranged. Every effort will be made to continue to follow participants who discontinue study medicine prematurely until the final study visit, if they are agreeable. Any participant who received at least one dose of pravastatin and is withdrawn or withdraws early from study treatment will undergo an early treatment discontinuation visit and will be requested to return for the applicable follow up visits. Evaluations at these visits will not include PK sampling.

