## ***Data Analysis***

The current study is a 2-week, 4-arm dose-escalation trial to determine the safety/tolerability and PK of pravastatin when co-administered with the standard drug regimen for drug-susceptible TB (Rifafour). Participants will receive standard anti-TB therapy and pravastatin beginning at a dose of 40 mg once daily. Each subsequent arm (pravastatin 80 mg, 120 mg, and 160 mg) of this study will continue to recruit participants until at least 10 participants in each group are evaluable for full PK analysis.

The primary endpoints in this study are safety/tolerability and pravastatin exposures. A regimen will be deemed safe and well tolerated if none of the participants require treatment discontinuation for a pravastatin-related adverse reaction and  $\leq 3$  participants experience a pravastatin-related grade 3 (or higher) adverse event during the 14-day study period and follow up. PK parameters (e.g., area under the concentration-time curve over 24 hours ( $AUC_{0-24}$ ), minimum concentration ( $C_{min}$ ), maximum concentration ( $C_{max}$ ), and oral clearance (Cl/F)), will be estimated for pravastatin from intensive sampling data after a single dose of pravastatin (baseline PK, prior to initiation of TB treatment) and after 14 days of co-administration with the first-line anti-TB regimen. Based on PK data of pravastatin when co-administered with rifampin ( $T_{max} = 1$  hour,  $T_{1/2} = 1.5$  hours), plasma samples will be collected for pravastatin measurements by LC-MS/MS at the following time points: pre-dose, 0.5 hrs, 1 hr, 1.5 hrs, 2 hrs, 3 hrs, 4 hrs, 6 hrs, and 8 hrs. Pravastatin exposures will be calculated using a noncompartmental approach using standard PK software, e.g., Phoenix WinNonLin. Using all PK data, a PK/PD model will be developed to evaluate the relationship between drug exposures (e.g.,  $C_{max}$ ,  $T_{max}$  or  $AUC_{0-24}$ ) and outcomes (e.g., safety/tolerability).  $C_{max}$  and  $t_{max}$  will be taken directly from the original data. The terminal log-linear phase of the plasma concentration-time curve will be identified visually for each curve.

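### Dose holds for Grade 2 clinical toxicity need not reach the adverse event form, and treatment stops are not classified by reason

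*Combined protocol and SAP*

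**What the plan says.** - **Holds.** Section 5, Other toxicities: for Grade 2, the participant is watched more closely and may have "study drugs temporarily held at the" discretion of the investigator. No maximum length is given.
- **Removal.** Section 9 lists reasons for immediate discontinuation. One is "Non-compliance with the study protocol (missing more than 2 doses of study drugs or not completing one of the PK sampling visits". It does not mention holds that the investigator ordered. The same section states: "Participants who prematurely discontinue study treatment after having received one or more doses of pravastatin will be replaced".
- **Adverse event form.** Section 5, Reporting, puts an event on the form only if it meets a listed requirement. The list includes "Any grade 3 or higher adverse event", "Study drug discontinuation due to an adverse event" and "Lab values that are considered clinically significant by the investigator", together with new medical diagnoses and pregnancy. Interruption of study drug is not on it.
- **Endpoints.** Section 4, Safety and Tolerability Endpoints: "Secondary endpoints include permanent discontinuation of assigned study regimen for any reason", except for ineligibility recognised later from culture or resistance results. The section also promises rates and types of toxicity that the investigator relates to study drugs, with no grade limit.
- **Dose decision.** Section 18, Data Analysis, calls a regimen safe only if "none of the participants require treatment discontinuation for a pravastatin-related adverse reaction", with a further limit on related events of Grade 3 or higher. The decision table in section 18 counts only Grade 3 or higher muscle, CK and liver events and has no term for discontinuation.

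**The concern.** Section 17 makes safety and tolerability the primary outcome, and section 2 says that the findings will inform the dose for a larger study. Whether participants can take the drug without a break for two weeks is a central part of tolerability. A Grade 2 clinical event serious enough for the investigator to interrupt the drug is direct evidence on that question, yet no item on the form list asks for it. The form's field for action taken with study drug is completed only once some other item has triggered the form.

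The second difficulty is classification. Section 9 puts missed doses and incomplete PK visits under one non-compliance label, and the plan does not say where a stop that follows a toxicity hold belongs. Section 4 then pools all stops in one secondary endpoint. A reader of the results could not separate intolerance from a missed sampling visit.

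**Working it through.** The plan states no figure on this point, so there is none to reproduce. The check sets the rules side by side and traces four cases. In cases A to C the event is a Grade 2 clinical toxicity, such as muscle pain, that is not reported as a new diagnosis. Section 9's threshold of more than two missed doses means three or more.

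| Case | AE form required (section 5, Reporting) | Data Analysis test (section 18) | Decision table (section 18) | Any-reason discontinuation (section 4) |
|---|---|---|---|---|
| A. Hold, then drug resumed, no stop | No | Not counted | Not counted | Not counted |
| B. Hold of 3+ doses, stop attributed to the event and to pravastatin | Yes | Counted; one is enough to fail | Not counted | Counted |
| C. As B, but held doses treated as missed and stop coded as non-compliance | No | Not counted | Not counted | Counted |
| D. Incomplete PK visit, stop under section 9 | No | Not counted | Not counted | Counted |

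1. **Case A is the firm gap.** It follows from the Reporting list alone and needs no miscoding. The end of Other toxicities points the same way: it asks for documentation on the form of toxicities graded 3 or 4 and is silent on Grade 2.
2. **Cases B and C differ only in coding.** The section 9 toxicity bullet refers back to the management rules of section 5. For CK and muscle symptoms, the mandatory stops there begin at Grade 3, so a Grade 2 muscle hold meets no listed muscle or CK stopping criterion. What remains is the investigator's safety bullet or the non-compliance bullet. Section 4 (Administration of study drug) measures adherence against prescribed doses but does not say whether a held dose is still prescribed.
3. **Cases C and D are treated alike** in every column.
4. **Liver events are largely outside the gap.** ALT above 3 times the upper limit with symptoms already forces a stop, liver events of that kind count in the cohort-initiation algorithm, and laboratory values can reach the form on the investigator's judgement.

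**Size.** One participant is 1/10 = 10% of an arm of 10, or 1/5 = 20% of the 40 mg arm. Let p be the chance that a participant has a pravastatin-related Grade 2 clinical event that leads to a hold of three or more doses and then a stop. The documents give no value, so p is assumed. The chance of at least one such participant among n is 1 − (1 − p)^n.

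| Assumed p | n = 5 | n = 10 |
|---|---|---|
| 5% | 1 − 0.95^5 = 23% | 1 − 0.95^10 = 40% |
| 10% | 1 − 0.90^5 = 41% | 1 − 0.90^10 = 65% |
| 20% | 1 − 0.80^5 = 67% | 1 − 0.80^10 = 89% |

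These are the chances that the choice between B and C arises at all in an arm. They are not estimates of how often it would be made wrongly.

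**The case against.** The case on the other side is substantial.

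- A hold that the protocol permits is compliance with it. The documents speak of held doses in one place and missed doses in another, so non-compliance is not the natural label for a stop after a hold. This stands: case C is one reading of an undefined term.
- If the toxicity causes the stop, the Reporting list requires a form at any grade, and the Data Analysis test fails the regimen if the reaction is related to pravastatin. This also stands.
- Section 5 opens by making investigators responsible for recording all adverse events, they are assessed daily, and a DSMB reviews each cohort's safety data before escalation. So the event should exist in source records. But Reporting limits which events go on the form, and the plan does not say that the DSMB or the final tables draw on anything wider.
- The primary safety endpoint in section 4 is Grade 3 or higher, so a Grade 2 hold was never meant to enter it. True, but the same section also promises drug-related toxicity without a grade limit.
- All-cause discontinuation is a common, conservative secondary endpoint and drives no dose decision. That justifies keeping it, but not leaving it unsplit. Section 4 does reschedule PK visits after missed or vomited doses, which narrows case D without removing it.

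A reader might infer that a tolerability failure can leave no trace in the dose decision. The documents do not support that as a general statement, because case B is caught. A reader might also infer that a missed PK visit counts in the opposite direction from a toxicity hold. It does not: both stops enter the any-reason endpoint, and if the hold-related stop is coded as non-compliance, neither enters the section 18 safety rules.

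**Conclusion.** The concern holds in a limited form. As written, the plan does not require the adverse event form for a Grade 2 clinical toxicity that interrupts study drug, so the safety data built from that form can miss it. This conclusion rests on the Reporting list alone, for events that are not also a new diagnosis, a significant laboratory value or the cause of a discontinuation.

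The effect on the dose decision is conditional. It needs held doses to be read as missed, the stop to be coded as non-compliance, and the Data Analysis test to govern. In that case the coding of a single participant can change whether a dose is called safe. If the decision table governs, coding makes no difference, because the table never counts a Grade 2 event or a discontinuation. The frequency is unknown; the percentages above rest on assumed rates.

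The point on incomplete PK visits is one of interpretation: stops that may have nothing to do with tolerability are pooled into a safety and tolerability endpoint with no breakdown.

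**What to change.** 1. Add to the mandatory list in section 5, Reporting: any adverse event leading to interruption of study drug.
2. Record the reason for every discontinuation, with a relatedness rating for any stop that follows a toxicity hold. Report the section 4 discontinuation endpoint overall and split into adverse-event-related and administrative reasons (non-compliance, incomplete PK visit, other).
3. Reconcile Other toxicities, section 9 and section 18 (Data Analysis) on whether held doses count as missed and how a resulting stop is classified. Which holding or stopping rule applies is for the sponsor and investigators; none is proposed here.

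The cost is protocol wording, one item in the reporting list and one table. The form already has a field for action taken with study drug. The downside is a few more forms and possibly a less favourable tolerability figure.

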**6. Blinding, including justification for blinding or not blinding the trial, if applicable.**

Not applicable

**7. Justification of why participants will not receive routine care or will have current therapy stopped.**

Not applicable

**8. Justification for inclusion of a placebo or non-treatment group.**

Not applicable

**9. Definition of treatment failure or participant removal criteria.**

Participants who prematurely discontinue study treatment after having received one or more doses of pravastatin will be replaced.

Study treatment must be immediately discontinued as a result of the following:

- Withdrawal of informed consent.
- Investigator considers it for safety reasons in the best interest of the participant that he/she be withdrawn.
- If a participant develops a new onset stage 4 illness after enrollment, they would meet the criteria for withdrawal from the study and, if HIV-positive, for fast track initiation of ART per the South African National Department of Health ART guidelines. The Interim WHO Clinical Staging of HIV/AIDS and HIV/AIDS Case Definitions for Surveillance, African Region (2005) will be used for guidance on definitions of stage 4 illnesses.
- Resistance to rifampin, as determined by GeneXpert.
- Participant experiences specific toxicities (including liver toxicity, CK elevation and myalgias and myopathy, as outlined in the "[Clinical Management of Adverse Events](#)" section)
- Participant becomes pregnant.
- Termination of the study by the Sponsor (US FDA, OHRP, or other relevant regulatory agencies)
- Non-compliance with the study protocol (missing more than 2 doses of study drugs or not completing one of the PK sampling visits)

All participants discontinuing study drug due to severe AE will remain in the study and continue to be monitored until the final scheduled clinic visit/laboratory evaluation. Their treatment will be referred to the local community TB clinics for standard anti-tuberculosis chemotherapy according to National Guidelines. The participants will be provided with a referral letter to take with them to the TB Clinic. Participants will be transported by the study staff to the clinic, or a follow-up call will be made by the study site staff to the clinic to determine if the participant attended the clinic on the date as arranged. Every effort will be made to continue to follow participants who discontinue study medicine prematurely until the final study visit, if they are agreeable. Any participant who received at least one dose of pravastatin and is withdrawn or withdraws early from study treatment will undergo an early treatment discontinuation visit and will be requested to return for the applicable follow up visits. Evaluations at these visits will not include PK sampling.

Patients will be encouraged at each visit to report new symptoms or illness experienced using a standardised checklist of questions which will be recorded in the source document that will also include participant attending other non-study health care workers or facilities since their last study visit.

All participants are provided with a 24 hour study phone number and are requested to report any adverse events to the site first before consulting any other health care facilities.

In the event that there has been a clinical consultation with a non-study health care worker or facility, the site will request a copy of the clinical records including results of investigations done and treatment prescribed. As soon as it is clinically appropriate, and in conjunction with the attending physician, the management of patients will be transferred to the study site. Any missed visit will trigger an assessment of a possible adverse event.

The most likely referral site for an admission to hospital is the adult wards at the Chris Hani Baragwanath Academic Hospital on the same campus as the research site. There is a good relationships with staff there and the site is frequently notified of study participant admissions. As soon as the site is notified of an admission either by the participant, their family or the attending doctor, they visit the patient in the ward at least daily.

***Description of what happens to participants receiving therapy when study ends or if a participant's participation in the study ends prematurely.***

Participants who withdraw from the trial after having received one or more doses of pravastatin or who are discontinued from the trial because of new recognition of participant ineligibility based on absence of *M. tuberculosis* growth in baseline sputum cultures, or growth of *M. tuberculosis* resistant to rifampin will be replaced. A participant may be prematurely withdrawn from the trial as a result of the following:

- At their own request or at the request of their legally acceptable representative.
- If, in the investigator's opinion, continuation in the trial would be detrimental to the well-being of the participant.
- At the specific request of the Sponsor (FDA, OHRP, or other regulatory agencies).

Every effort will be made to reduce loss to follow-up. Participants will be contacted by phone if they do not return for study visits.

To ascertain the reason why patients have not returned for a scheduled study visit we will do the following:

Participants will be contacted telephonically as soon as it becomes apparent, on the day of the scheduled visit, that they will not be attending the study visit, usually by noon of the day of the visit. The site's usual practice is to identify at least three contact numbers which are tested at least once at each face-to face visit. The site will routinely call or text participants a day prior to their scheduled visit to remind them thereof. If they are able to contact the patient on any of the three numbers, they will ascertain the reason for the visit non-attendance, and if it is an issue with transport they will attempt to resolve this by making an offer for the study site to collect the participant. The site will also ask if there are any other reasons for non-attendance. A script for telephonic contacts of this nature will be drafted to ensure that questions are asked about possible adverse events that may have occurred and prevented a participant from attending the scheduled study visit.

In the event that the telephonic contact, that day is unsuccessful, study staff will call the next day, on at least two occasions following the same process as above.

If the patient is uncontactable a day after the visit, a home visit will be made later that day to contact the patient.

All participants withdrawn will be referred to the local community TB clinics for standard anti-tuberculosis chemotherapy according to National Guidelines. The participants will be provided with a referral letter to take with them to the TB Clinic. The participants will either be transported to the clinic by the study staff, or else a follow-up call will be made by the study site staff to the clinic to determine if the participant attended the clinic on the date as arranged.

